3.1.9. Criteria for Dose Escalation

No dose escalation of mogamulizumab is foreseen for the estimation of the combination MTD. Dose escalation and de-escalation of PF-05082566 will follow the Time-to-Event Continual Reassessment Method (TITE-CRM)^[28,33] up to 5 mg/kg.

A flat dosing of PF-05082566 100 mg will be studied to confirm the safety and PK at a dose that may be used for the expansion cohorts. The safety data at 100 mg flat dose (equivalent to 1.2 mg/kg) will be pooled together with the data at 1.2 mg/kg in the TITE-CRM model.

The 5.0 mg/kg cohort (if safe and tolerable) will enroll at least 6 squamous NSCLC patients to determine RP2D.

In each cohort, 3 to 9 patients evaluable for MTD determination may be enrolled.

The first 3 patients (Dose Level 1) will be treated at the starting dose. For each subsequent patient, the probability of DLT is estimated for each level based on all the collected data from all treated patients up to that time and the prior expectations of toxicity, and the patient is assigned to the currently estimated target level (with escalation restrictions as indicated below), defined as the dose having an estimated probability of DLT closest to but not greater than the target rate (30%).

The probabilities of toxicity are estimated based on a Bayesian statistical model to learn about the overall dose-toxicity relationship.

Patients' DLT data will be reported to the study statistician who will update the dose-toxicity model before the next enrolled patient is treated.

The MTD is defined as the highest combination dose with a DLT rate <30% from the model estimate (see [Section 9.2](#)).

Dose escalation may stop if:

- Maximum sample size (n=30, see [Section 9.2](#)) is reached; or
- 9 DLT evaluable patients have been treated at the estimated MTD (6 if no DLT observed at any dose); or
- All doses appear to be overly toxic and the MTD cannot be determined in the current trial.

In the TITE-CRM paradigm, patients who have enrolled in the trial, but have not experienced DLT, will be included in the probability calculation with an initial weight equal to the proportion of the 8-week (2 cycles of PF-05082566 and mogamulizumab) DLT observation period that the patients have completed (however, the weight function may be modified if accumulating safety data suggest a different pattern).

Patients who experience DLT or complete the observation period without DLT will be assigned full weight (=1).

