Details on the TITE-CRM method are provided in [Section 9.2](#) and the Statistical Analysis Plan (SAP).

To avoid overly rapid escalation and to retain the efficiency of dose administration when enrollment is fast, the following restrictions and practical considerations will be followed.

- Dose skipping in escalation to untested doses is not allowed ($k \rightarrow k+1$). In particular, at least three patients should have been treated at dose level k before escalation to dose level $k+1$;
- At least three patients should have been on treatment (for a minimum of 3 weeks) and observed DLT rate <33% at dose level k before a patient is assigned to dose level $k+1$ (*Note that the waiting window depends on our knowledge in the time-to-event pattern of toxicity and accumulating safety data, and thereby the confidence in the associated weights. However, intentional delay in enrollment in the absence of DLT or serious AEs should be minimized and discouraged*);
- Dose escalation recommendation by the TITE-CRM algorithm may be overruled by the Sponsor if the nature of the existing data causes safety concern.

Dose escalation and de-escalation will be carried out according to [Table 6](#).

Table 6. Dose Escalation and De-Escalation Cohorts

Dose Levels	PF-05082566 Doses* (mg/kg)	Mogamulizumab Doses (mg/kg)
Dose Level 3	5	1
Dose Level 2	2.4	1
Dose Level 1a**	100 mg flat dose	1
Dose Level 1 (starting dose)	1.2	1
Dose Level -1	1.2	0.5
Dose Level -1a***	50 mg flat dose	1

* Intermediate dose levels could be used for dose de-escalation based on DLTs observed.

** This cohort can be dosed simultaneously with any other dose cohort..

*** To be used for dose reductions for those on the 100 mg flat dose cohort.

Occurrence of DLTs during the exploration of Dose Level (DL) 1 will require reduction of mogamulizumab to 0.5 mg/kg (ie, DL -1). If Dose Level -1 is tolerated with no DLTs, then dose escalation of PF-05082566 will continue according to the table above, maintaining mogamulizumab at 0.5 mg/kg until an MTD is reached and/or the PF-05082566 dose is escalated to the highest planned dose of 5 mg/kg.

Intra-patient dose escalation will not be permitted.

Cumulative safety data will continue to be evaluated at the estimated MTD in the expansion cohorts using the Bayesian statistical model. Should emerging data in the expansion cohorts indicate that the selected dose is more toxic than previously estimated (DLT rate >30%) or in case of exposure plateau **CC1**

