3.4. Baseline Variables

3.4.1. Study Drug, Study Treatment and Baseline Definitions

In this study, ‘study drug’ refers to PF-05082566 or mogamulizumab and ‘study treatment’ (or ‘treatment group’) refers to one of the following:

- Dose Level -1: PF-05082566 1.2 mg/kg q4wks + mogamulizumab 0.5 mg/kg;
- Dose Level 1: PF-05082566 1.2 mg/kg q4wks + mogamulizumab 1 mg/kg;
- Dose Level 1a: PF-05082566 100 mg q4wks + mogamulizumab 1 mg/kg;
- Dose Level 2: PF-05082566 2.4 mg/kg q4wks + mogamulizumab 1 mg/kg;
- Dose Level 3: PF-05082566 5 mg/kg q4wks + mogamulizumab 1 mg/kg.

Start and end dates of study treatment:

The date/time of first dose of study treatment is the earliest date/time of the first non-zero dose date/time for the study drugs in the combination.

The date/time of last dose of study treatment is the latest date/time of the last non-zero dose date/time for the study drugs in the combination.

Definition of baseline:

The last available assessment prior to the start of study treatment is defined as ‘baseline’ value or ‘baseline’ assessment for safety and efficacy analyses. If an assessment is planned to be performed prior to the first dose of study treatment in the protocol and the assessment is performed on the same day as the first dose of study treatment, it will be assumed that it was performed prior to study treatment administration, if assessment time point is not collected or is missing. If assessment time points are collected, the observed time point will be used to determine pre-dose on study day 1 for baseline calculation. Unscheduled assessments will be used in the determination of baseline. However, if time is missing, an unscheduled assessment on study day 1 will be considered to have been obtained after study treatment administration.

Patients who start treatment and discontinue from the study on the same day may have two different sets of data collected on study day 1 (one during study and one in the End of Treatment (EOT) visit. Data reported at the EOT visit are not eligible for baseline selection.

If a scheduled pre-dose measurement actually occurred post-dose, then the corresponding measurement will be treated and analyzed similar to an unscheduled post-dose measurement.

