The MTD is defined as highest dose that is associated with a DLT rate <30%. A power function modeling DLT rate at each dose d_i ($i=1, \dots, 4$) expressed as $\text{Pr}(\text{DLT} | d_i) = F_i(\beta)$ will be used:

[figure not shown]
$$F_i(\beta) = p_i^{\exp(\beta)}$$

where p_i is the prior estimate of DLT rate at dose level d_i , and $p_1 \leq p_2 \leq \dots \leq p_4$. These estimates will be projected based model sensitivity to DLTs, together with single agent safety data for both study drugs. β is an unknown single parameter modeling the dose-toxicity relationship, with prior distribution $N(0, \sigma_0^2)$, where σ_0 is the standard deviation of the normal prior distribution with mean=0. At the beginning of the trial, the initial prior value of β is set as 0, the prior mean, which gives a prior dose-toxicity model of $F_i(\beta) = p_i$ based on the power function.

In the Bayesian paradigm, the prior distribution $N(0, \sigma_0^2)$ expresses the researchers' belief in the quality of the initial estimates p_i . The smaller the standard deviation σ_0 , the more confidence researchers have in the precision of p_i , and vice versa. As the trial progresses, this prior distribution is combined mathematically with the observed data to yield the posterior distribution of the parameter β (the posterior mean of β will be calculated to model the dose-toxicity relationship). The prior distribution determines how responsive TITE-CRM is to the accumulated data. With a small σ_0 upfront, the posterior toxicity probability

estimates remain close to the prior estimates unless significantly discrepant data otherwise occur; with a large σ_0 , the model will tend to be more immediately responsive to data. In this trial, $\sigma_0=1$, which provides a reasonably flat prior distribution of β , with 90% Bayesian credible interval of $\exp(\beta) : [0.19, 5.21]$, sufficiently wide to cover a wide spectrum of dose-toxicity scenarios. Figure 1 illustrates the dose-toxicity curve (blue curve) with 90% upper and lower bounds (red curves) when the initial prior estimates p_i are (0.095, 0.186, 0.300, 0.422).

Figure 1. Example Plot of Prior Dose Toxicity Curve

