5.2. General Methods

As described in [Section 3.4](#), in this study ‘**treatment group**’ refers to one of the following:

- Dose Level -1: PF-05082566 1.2 mg/kg q4wks + mogamulizumab 0.5 mg/kg;
- Dose Level 1: PF-05082566 1.2 mg/kg q4wks + mogamulizumab 1 mg/kg;
- Dose Level 1a: PF-05082566 100 mg q4wks + mogamulizumab 1 mg/kg;
- Dose Level 2: PF-05082566 2.4 mg/kg q4wks + mogamulizumab 1 mg/kg;
- Dose Level 3: PF-05082566 5 mg/kg q4wks + mogamulizumab 1 mg/kg.

Baseline characteristics, disposition and efficacy data will be summarized based on the FAS by treatment group.

DLTs will be summarized based on the DLT-evaluable set by treatment group.

Other safety data, exposure data, concomitant medications and non-drug treatments will be summarized based on the safety analysis set by treatment group.

PK data will be summarized based on the PK analysis sets by treatment group.

CCI

Immunogenicity data will be summarized based on the immunogenicity analysis set by treatment group.

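### If PF-05082566 is escalated on mogamulizumab 0.5 mg/kg, the dose-finding model as written cannot tell those combinations from the 1 mg/kg ones, and the SAP has no group for two of them

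*Protocol*

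**What the plan says.** **The branch.** Protocol 3.1.9: "Occurrence of DLTs during the exploration of Dose Level (DL) 1 will require reduction of mogamulizumab to 0.5 mg/kg". If Level -1 shows no DLTs, PF-05082566 escalation "will continue according to the table above, maintaining mogamulizumab at 0.5 mg/kg until an MTD is reached" or its highest planned dose of 5 mg/kg is given. This is a written route to 2.4+0.5 and 5+0.5 mg/kg (PF-05082566 + mogamulizumab). Table 6 pairs 0.5 mg/kg only with PF-05082566 1.2 mg/kg.

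**The data.** In the same section, "the probability of DLT is estimated for each level based on all the collected data from all treated patients up to that time". On the flat-dose cohort, which receives mogamulizumab 1 mg/kg: "The safety data at 100 mg flat dose (equivalent to 1.2 mg/kg) will be pooled together with the data at 1.2 mg/kg". A footnote to Table 6 adds: "This cohort can be dosed simultaneously with any other dose cohort".

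**The model.** Protocol 9.2 and SAP 5.1.2 use F_i(β) = p_i^exp(β) with a single β and four ordered levels, "where p_i is the prior estimate of DLT rate at dose level d_i". The available levels are listed by PF-05082566 dose alone: 1.2, 2.4, 100 mg flat (treated as equal to 1.2) and 5.0. There is no mogamulizumab term. The MTD is nevertheless defined in Protocol 3.1.9 and 3.3 as a combination dose.

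**The reporting groups.** SAP 3.4.1 and 5.2 define five treatment groups. Mogamulizumab 0.5 mg/kg appears in one: "Dose Level -1: PF-05082566 1.2 mg/kg q4wks + mogamulizumab 0.5 mg/kg". The groups for the higher PF-05082566 doses carry 1 mg/kg, for example "Dose Level 2: PF-05082566 2.4 mg/kg q4wks + mogamulizumab 1 mg/kg". DLT, other safety, efficacy, PK and immunogenicity summaries all use these groups.

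**The concern.** The primary objective is a combination MTD, but the model does not distinguish combinations. Read literally, the DLTs at 1.2+1 that open the branch stay in the estimates for 2.4+0.5 and 5+0.5. In the other direction, DLT-free patients on 0.5 mg/kg lower the estimates for combinations with 1 mg/kg. The second effect is practical, because the flat cohort at 1 mg/kg may be recruiting at the same time.

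One increasing list of p_i also needs an order between 1.2+1 and 2.4+0.5. Neither document gives one. At stake are which level is read as below 30%, what the declared MTD refers to, and where branch patients appear in the tables.

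**Working it through.** **1. The plan's own prior figures.** With σ₀ = 1, the 90% interval of exp(β) is exp(±1.645) = 0.193 to 5.18. The documents state 0.19 to 5.21; exp(1.65) = 5.21, so this is rounding. The example rates (0.095, 0.186, 0.300, 0.422) follow from an indifference-interval calibration at target 0.30 and half-width 0.06: r = ln 0.24 / ln 0.36 = 1.397, and 0.30^(r²), 0.30^r, 0.30, 0.30^(1/r) give the four values. The prior is understood as the plan intends.

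**2. Which levels are the four?** The documents do not settle this. Protocol 9.2 lists PF-05082566 doses, but pooling the flat dose leaves three. Table 6 without 1a and -1a has four combinations: -1, 1, 2 and 3. Three mappings were run:

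- M1: 1.2, 2.4, 5 mg/kg at 0.095, 0.186, 0.300
- M2: 1.2, 2.4, 5 mg/kg at 0.186, 0.300, 0.422
- M3: Levels -1, 1, 2, 3 at 0.095, 0.186, 0.300, 0.422

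M1 and M2 give 1.2+1 and 1.2+0.5 the same p_i. M3 separates those two, but 2.4+0.5 still shares a p_i with 2.4+1, and 5+0.5 with 5+1.

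**3. Method.** β ~ N(0,1); the posterior mean of β is found by grid integration and plugged into F_i. All patients have full weight. DLT counts are assumed for illustration.

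Example (M1; 2/6 at 1.2+1, 0/3 at 1.2+0.5):
- All patients: E[β] = -0.421, exp = 0.656, F(2.4) = 0.186^0.656 = 0.33.
- 0.5 mg/kg only: E[β] = 0.489, exp = 1.631, F(2.4) = 0.186^1.631 = 0.06.

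**4. Estimate at 2.4 mg/kg just after Level -1 (all patients vs 0.5 mg/kg only, %).**

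| Level 1, then Level -1 | M1 | M2 | M3 |
|---|---|---|---|
| 1/3, 0/3 | 27 vs 6 | 29.7 vs 11 | 33 vs 14 |
| 1/3, 0/6 | 21 vs 4 | 23 vs 6 | 27 vs 9 |
| 2/3, 0/3 | 42 vs 6 | 45 vs 11 | 47 vs 14 |
| 2/3, 0/6 | 33 vs 4 | 35 vs 6 | 39 vs 9 |
| 2/6, 0/3 | 33 vs 6 | 35 vs 11 | 37 vs 14 |
| 2/6, 0/6 | 28 vs 4 | 29 vs 6 | 32 vs 9 |
| 3/6, 0/3 | 43 vs 6 | 45 vs 11 | 47 vs 14 |
| 3/6, 0/6 | 36 vs 4 | 38 vs 6 | 41 vs 9 |

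The gap runs from 17 points (M2; 1/3, 0/6: 0.228 - 0.059) to 37 points (M1; 3/6, 0/3: 0.433 - 0.064). The pooled estimate is above 30% in 17 of the 24 cells; the 0.5-only estimate never is.

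**5. Later in the branch.** The gap narrows as branch patients accrue. After 0/6, 0/3 and 1/6 at 1.2, 2.4 and 5 mg/kg, all with 0.5, it is 8 to 19 points at 2.4 mg/kg. After 0/3, 0/3 and 0/6 (M1), the pooled estimate at 5 mg/kg is 19%, 27% or 34% following 1/3, 2/6 or 3/6 at Level 1, against 2% from the branch alone. Only the 3/6 case is above 30%.

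**6. The reverse direction (M1).** After 3/6 at 1.2+1 alone, the estimates are 43% at 1.2 and 54% at 2.4 mg/kg. Adding the same 12 DLT-free patients on 0.5 mg/kg moves them to 12% and 23%, although nothing new was observed at 1 mg/kg.

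**The case against.** The strongest reply is that the plan is silent here rather than wrong. The sentence on using all treated patients describes ordinary CRM updating. The p_i are to be projected from safety data, and the values shown illustrate a plot. Re-specifying the prior or the data set at the switch is not excluded. This stands: a reader might infer that the plan prescribes a false pooled estimate, and the documents do not go that far. They do give a literal rule that pools, and nothing that replaces it.

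The 0.5-only figures are also no benchmark. They ignore every DLT already seen with these two drugs, so a large gap partly measures discarded information. In the early cases, pooling errs towards caution. Both points stand, except that step 6 shows the opposite direction for 1 mg/kg.

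It is tempting to say that pooling blocks the escalation that the protocol says continues. That is true in some cells and false in others. The 3/6 inputs are extreme, since any DLTs at Level 1 already call for the reduction.

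Finally, a reader might infer that branch patients would be tabulated under the wrong mogamulizumab dose. SAP 4.1 and 4.2 classify by treatment actually received, and the exposure derivations in SAP 6.5.3 allow 0.5 mg/kg. These patients have no group rather than a wrong one, and Level -1 itself has a group.

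**Conclusion.** The point holds in a limited form. The protocol contains a defined path to 2.4+0.5 and 5+0.5 mg/kg. The model as written cannot distinguish these from the 1 mg/kg combinations, no order between 1.2+1 and 2.4+0.5 is given, and the SAP has no group for either new combination. Followed literally, the estimates belong to neither mogamulizumab dose.

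The handling can move the 2.4 mg/kg estimate by 17 to 37 points when the branch decision is made, enough to change which level is below 30% in some cases but not all. The documents do not show which estimate is nearer the truth.

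This rests on assumed DLT counts, the example prior rates, an inferred mapping of levels and full weights in place of time-to-event weights. It matters only if DLTs occur at Level 1 and Level -1 is then tolerated. If the branch is never opened, the results are unaffected.

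**What to change.** Reconcile Protocol 3.1.9 (with Table 6) and 9.2 with SAP 3.4.1, 5.1.2 and 5.2. Specifically:

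- In Protocol 9.2 and SAP 5.1.2, say which combinations the four p_i refer to, and do not let patients on different mogamulizumab doses share one p_i.
- Limit the pooling of the 100 mg flat cohort with 1.2 mg/kg to patients on the same mogamulizumab dose.
- Prespecify how 1 mg/kg data and prior rates enter the estimates for the 0.5 mg/kg combinations. A separate fit is one option; its cost is fewer patients and no use of the DLTs seen at 1 mg/kg. Down-weighting, a mogamulizumab term or a re-specified list of prior rates are others.
- State each MTD with its mogamulizumab dose.
- Add 2.4+0.5 and 5+0.5 mg/kg as treatment groups in SAP 3.4.1 and 5.2.

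The cost is wording and two table columns. Because the method bears on the primary endpoint's analysis, Protocol section 9 may require an amendment. The choice affects dose allocation, so the sponsor should make it before the branch opens. No dose or escalation rule is proposed here.

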3.2. DLT Definition

Severity of AEs will be graded according to CTCAE version 4.03. For the purpose of dose escalation, any of the following AEs occurring during the DLT observation period (first 2 Cycles, ie, 8 weeks) that are attributable to one or both study drugs will be classified as DLTs:

Hematologic

- Grade 4 neutropenia lasting >7 days;

- Febrile neutropenia, defined as absolute neutrophil count (ANC) $<1000/\text{mm}^3$ with a single temperature of >38.3 degrees C (101 degrees F) or a sustained temperature of ≥ 38 degrees C (100.4 degrees F) for more than one hour;
- Grade ≥ 3 neutropenic infection;
- Grade ≥ 3 thrombocytopenia with bleeding;
- Grade 4 thrombocytopenia.

Non-Hematologic:

- Grade ≥ 3 non laboratory toxicities (excluding infusion reactions), except those that have not been maximally treated (eg, nausea, vomiting, diarrhea).
- Grade ≥ 3 laboratory abnormalities (other than AST/ALT) if:
 - Medical intervention is required to treat the patient, or
 - The abnormality leads to hospitalization.
- Grade 4 aspartate aminotransferase (AST) and alanine aminotransferase (ALT) increase.

3.3. MTD Definition

The MTD is defined as the highest combination dose with a DLT rate $<30\%$ from the TITE-CRM model estimate (see details in [Section 9.2](#)).

Once the MTD is estimated, additional patients may be enrolled at this dosing level. In the expansion cohort, patients' DLT data will be entered into the Bayesian statistical model of the TITE-CRM procedure. If the posterior distribution of the model incorporating the additional data from the expansion cohort suggest the estimated MTD is associated with a higher than expected DLT rate the next lower dose or an intermediate dose level will be expanded, and may be declared as the RP2D.

3.4. Dose for Expansion Cohorts

The expansion cohort(s) will be tested at either the estimated MTD or lower doses based on the emerging safety, efficacy and PK/PD data.

3.5. Dose Expansion Portion

Expansion cohort(s) will test PF-05082566 in combination with mogamulizumab in patients with select advanced solid tumors. Tumor types for the expansion cohorts will be selected from CRC, bladder, ovarian, squamous esophageal, SCCHN and/or squamous NSCLC. The PF-05082566 dose for expansion cohorts may be a flat dose of 100 mg. All patients in the expansion cohorts may be enrolled simultaneously. The total number of patients enrolled

into one or more expansion cohorts will be determined based on the tumor type, and patient population emerging data from this study. PK/ADA samples will be collected from all evaluable patients in the dose expansion cohorts.

3.6. Recommended Phase 2 Dose (RP2D) Definition

The RP2D is the dose chosen for further study based on Phase 1 results. If the MTD proves to be clinically feasible for long term administration in a reasonable number of patients, such dose usually becomes the RP2D. Further experience with the MTD may result in a RP2D dose lower than the MTD.

4. PATIENT SELECTION

This study can fulfill its objectives only if appropriate patients are enrolled. The following eligibility criteria are designed to select patients for whom protocol treatment is considered appropriate. All relevant medical and non-medical conditions should be taken into consideration when deciding whether this protocol is suitable for a particular patient.

Patient eligibility should be reviewed and documented by an appropriate member of the investigator's study team before patients are included in the study.

4.1. Inclusion Criteria

Patients must meet all of the following inclusion criteria to be eligible for enrollment into the study:

1. Histological or cytological diagnosis of advanced/metastatic solid tumor malignancy. Dose Finding Cohorts: Tumor types will be limited to CRC, SCCHN, squamous NSCLC, bladder, or ovarian carcinomas which have progressed on standard therapy, or for which no standard therapy is available. Expansion Cohorts: Tumor types may include: Histological or cytological diagnosis of either advanced/metastatic CRC, bladder, ovarian, squamous esophageal, SCCHN, or squamous NSCLC. **NOTE:** Final determination of tumor types for expansion will be made based on emerging data from the dose-finding portion of the study or obtained from ongoing studies testing PF-05082566.
2. Measurable disease by RECIST version 1.1.
3. For Expansion Cohorts only: patients must have tumor accessible for biopsies (core needle biopsy or excision preferred). See [Section 3.1.7](#).
4. Age ≥ 18 years.
5. Eastern Cooperative Oncology Group (ECOG) performance status of 0 or 1.
6. Adequate bone marrow function, defined as follows:
 - absolute neutrophil count (ANC) $\geq 1.5 \times 10^9/L$ ($\geq 1,500/\mu L$);

- platelet (PLT) count $\geq 75 \times 10^9/L$ ($\geq 75,000/\mu L$);
- hemoglobin (Hb) $\geq 9.0 \text{ g/dL}$ ($\geq 5.6 \text{ mmol/L}$).

Patients must be transfusion independent (ie, no blood product transfusions for a period of at least 14 days prior to study registration).

7. Adequate renal function, including:

- serum creatinine $\leq 1.5 \times$ upper limit of normal (ULN); **OR**
- estimated creatinine clearance $\geq 60 \text{ mL/min}$ as calculated using the method standard for the institution.

8. Adequate liver function, including:

- Total serum bilirubin $\leq 1.5 \times$ ULN (unless the patient has documented Gilbert syndrome);
- Aspartate and Alanine aminotransferase (AST & ALT) $\leq 2.5 \times$ ULN;
- Alkaline phosphatase $\leq 2.5 \times$ ULN; ($\leq 5 \times$ ULN in case of bone metastasis).

9. Resolved acute effects of any prior therapy to baseline severity or CTCAE Grade ≤ 1 except for AEs not constituting a safety risk by investigator judgment.

10. Serum/urine pregnancy test (for females of childbearing potential) negative at screening and before the patient will receive the study treatment.

11. Male and female patients of childbearing potential and at risk for pregnancy must agree to use two (2) highly effective methods of contraception throughout the study and for 60 days after the last dose of assigned study treatment.

12. Female patients who are not of childbearing potential (ie, meet at least one of the following criteria):

- Have undergone a documented hysterectomy and/or bilateral oophorectomy;
- Have medically confirmed ovarian failure; **OR**
- Achieved post-menopausal status, defined as follows: cessation of regular menses for at least 12 consecutive months with no alternative pathological or physiological cause; and have a serum follicle stimulating hormone (FSH) level within the laboratory's reference range for postmenopausal women.

13. Evidence of a personally signed and dated informed consent document indicating that the patient has been informed of all pertinent aspects of the study.

14. Patients who are willing and able to comply with scheduled visits, treatment plans, laboratory tests and other procedures.

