1. INTRODUCTION

1.1. Mechanism of Action/Indication

PF-05082566 is a novel fully human IgG2 monoclonal anti-body (mAb) agonist of 4-1BB (CCI [REDACTED], TNFRSF9) that is being developed in combination with Poteligeo® (mogamulizumab), a recombinant humanized mAb targeting C-C chemokine receptor 4, (CCR4, CD194) registered in Japan for CCR4 expressing adult T-cell leukemia/lymphoma (ATL), peripheral T-cell lymphoma (PTCL) and cutaneous T-cell lymphoma (CTCL). The proposed combination is being studied for the treatment of adult patients with advanced solid malignancies that are unresponsive to currently available therapies, or for whom no standard therapy is available.

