4.2. Exclusion Criteria

Patients presenting with any of the following will not be included in the study:

1. Central nervous system primary malignancies, active seizure disorder or spinal cord compression, or carcinomatous meningitis. Patients with previously treated brain metastases may participate provided they are stable (without evidence of progression by imaging for at least 4 weeks prior to registration and any neurologic symptoms have returned to baseline), have no evidence of new or progressing brain metastases. This exception does not include carcinomatous meningitis, which is excluded regardless of clinical stability.
2. Systemic anticancer therapy within 28 days prior to registration. In absence of persisting toxicity, 5 half-lives since completion of prior anti-cancer therapy is acceptable.
3. Therapeutic or experimental monoclonal antibodies within 60 days prior to registration.
4. Systemic corticosteroid therapy or any other form of immunosuppressive therapy within 14 days prior to registration. Patients that require intermittent use of bronchodilators, inhaled steroids, or local steroid injections will not be excluded from the study.
5. Major surgery within 28 days prior to registration.
6. Radiation therapy within 14 days prior to registration.
7. History of, or active ethanol abuse or hepatitis (eg, alcohol or non-alcohol steatohepatitis [NASH], drug related, auto immune, virally related).
8. Live vaccine within 30 days prior to registration.
9. Active and clinically significant bacterial, fungal or viral infection including hepatitis B (HBV), hepatitis C (HCV), known human immunodeficiency virus (HIV) or acquired immunodeficiency syndrome (AIDS) related illness (HIV testing is not required), including patients who have an active infection requiring systemic therapy. Active herpes simplex or herpes zoster. Patients on prophylaxis for herpes infection who started taking medication at least 30 days prior to study entry, and have no active signs of active infection, and whose last active infection was more than 6 months prior to registration, may enter the study, and should continue to take the prescribed medication for the duration of the study.

10. Known prior or suspected hypersensitivity to study drugs or any component in their formulations (including patients who are known to be positive for ADA to mogamulizumab or PF-05082566).

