6.4. Subset Analyses

The number of patients expected in each treatment group is small and therefore no subset analyses are planned in this study.

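### Inclusion criterion 1 requires failed or unavailable standard therapy only for the dose-finding cohorts, so expansion eligibility is wider than the population stated in Protocol Section 1.1

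*Protocol*

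**What the plan says.** Protocol Section 1.1 gives the population for the combination as "adult patients with advanced solid malignancies that are unresponsive to currently available therapies, or for whom no standard therapy is available". It draws no line between dose finding and expansion.

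Criterion 1 in Protocol Section 4.1 has three parts:

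- A common stem: "Histological or cytological diagnosis of advanced/metastatic solid tumor malignancy".
- A dose-finding sentence, which lists tumor types and ends with the condition "carcinomas which have progressed on standard therapy, or for which no standard therapy is available".
- A separate expansion sentence: "Expansion Cohorts: Tumor types may include: Histological or cytological diagnosis of either advanced/metastatic CRC, bladder, ovarian, squamous esophageal, SCCHN, or squamous NSCLC".

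A note after the expansion sentence leaves the final choice of tumor types to emerging data. It does not mention prior therapy.

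Protocol Section 3.5 describes the expansion population only by disease: "Expansion cohort(s) will test PF-05082566 in combination with mogamulizumab in patients with select advanced solid tumors". Section 3.1.2 and SAP Section 2.2 likewise give a tumor list. On subgroups, SAP Section 6.4 says: "The number of patients expected in each treatment group is small and therefore no subset analyses are planned in this study".

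**The concern.** The eligibility criteria are what a site applies. If the prior-therapy condition is missing from the expansion sentence, a patient with newly diagnosed metastatic disease of a listed type, and standard treatment still untried, satisfies criterion 1. Such a patient lies outside the population in Section 1.1, yet enrolling that patient would not be a protocol deviation.

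Two things are at stake. The first is patient protection. The protocol itself treats forgone therapy as a serious matter: Section 5.4.5 requires fresh consent before dosing continues past initial progression, because the patient may be giving up an approved treatment. The visible text has no parallel safeguard at entry to expansion.

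The second is interpretation. The expansion cohorts supply DR, TTR and PFS and contribute to objective response. If prior-treatment status varies among those patients, or differs from that of the dose-finding patients, the summaries describe a mixed population that the plan neither names nor separates.

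**Working it through.** The plan gives no figure to reproduce here. The check is a comparison of texts, followed by one ratio for scale.

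**Step 1. Where the condition appears.**

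| Place | Prior-therapy condition for expansion? |
|---|---|
| Protocol 1.1 | Stated for the combination as a whole, but as intent, not as an eligibility rule |
| Protocol 4.1, criterion 1, stem | None |
| Protocol 4.1, criterion 1, dose-finding sentence | Present, but attached to the dose-finding tumor list |
| Protocol 4.1, criterion 1, expansion sentence | None |
| Protocol 3.1.2 (visible text) and 3.5 | None; tumor types only |
| SAP 2.2, dose-expansion text | None; tumor types only |

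**Step 2. Whether another criterion supplies it indirectly.**

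- Inclusion criterion 9 asks that acute effects of earlier treatment have resolved. It does not require that there was any.
- Exclusion criterion 2, which begins "Systemic anticancer therapy within 28 days prior to registration", and exclusion criterion 3 on monoclonal antibodies are washout rules. An untreated patient passes both.
- SAP Section 2.2 restricts some patients to disease relapsed on or refractory to PD-1/PD-L1 treatment, but only in the 100 mg flat-dose and 5.0 mg/kg dose-finding cohorts.
- The opening of Protocol Section 4 asks for judgment about suitability, and Section 5.1 requires the sponsor to confirm each enrolment. Neither states a prior-therapy rule.

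Nothing in Steps 1 and 2 makes failed or unavailable standard therapy a condition of expansion entry.

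**Step 3. How many patients the sentence governs.** Protocol Section 3.1.2 allows up to 40 response-evaluable expansion patients, and the protocol expects about 70 patients overall. The share is 40 / 70 = 0.571, or about 57%. This is the number entering under the unrestricted sentence. It is not an estimate of how many would be untreated.

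**Step 4. What the analysis would show.** SAP Sections 3.4.1 and 5.2 define treatment groups by dose level, with no separate label for expansion, and efficacy is summarized by those groups. SAP Section 6.5.1.4 tabulates and lists prior therapy as a baseline characteristic. Protocol Section 9.4 lists response by patient. No section crosses response, DR or PFS with prior-therapy status, and SAP Section 6.4 rules out subset analyses.

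**The case against.** The strongest reply is that this is a drafting slip with little practical reach. The sponsor must confirm each enrolment in writing, eligibility must be reviewed and documented, and the expansion population is openly provisional. SAP Section 6.5.1.4 also has no zero category when it counts prior drug regimens, which suggests that its authors expected pretreated patients. Efficacy is secondary and descriptive, with no hypothesis test. All of that is fair. It makes such enrolment less likely, but it does not put the missing condition into the rule that sites and the sponsor would apply.

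Parts of the protocol near this point are redacted, including Section 3.1.7 and some of Section 3.1.2. The finding is therefore limited to the visible text.

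A reader might infer several stronger things that the documents do not support:

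- **That untreated patients were meant to be enrolled.** The text permits it. Nothing shows that it was planned.
- **That expansion results could not be interpreted at all.** Prior therapy and response are both listed by patient, so untreated responders could be identified by linking the listings. What is missing is a planned summary.
- **That the response rate would be inflated by a known amount.** The documents give no response rates by prior-therapy status and no expected share of untreated patients, so no size can be attached.
- **That the MTD is compromised.** Protocol Section 3.3 does feed expansion DLTs into the dose-toxicity model, but nothing in the documents links DLT risk to prior therapy.

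**Conclusion.** Criterion 1 is wrong as written when set against Section 1.1. The operative rule for up to 40 of about 70 patients omits a condition that the protocol states for the combination as a whole and enforces only in dose finding. This is an inconsistency in an eligibility rule, not a missing detail.

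The effect on expansion ORR, DR and PFS is a possible mixing of untreated and pretreated patients. Its size is unknown, and it could be zero if sites and the sponsor apply the Section 1.1 population in practice.

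The conclusion rests on two assumptions: that redacted text does not supply the condition, and that Section 1.1 describes both portions, as its wording suggests. The documents do not say whether the wider expansion wording was deliberate. If it was, Section 1.1 is the text that is wrong. Either way the two sections do not agree.

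**What to change.** Reconcile criterion 1 in Protocol Section 4.1 with Section 1.1.

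- **Default:** extend the clause already in the dose-finding sentence to the expansion sentence of criterion 1. Repeating it in Protocol Section 3.5 and SAP Section 2.2 is optional.
- **If a broader expansion population is intended:** say so and justify it in the protocol, amend Section 1.1, and add to the SAP a descriptive report of expansion ORR, DR and PFS by prior-therapy status, as an exception to Section 6.4.

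The default costs one clause in an amendment, in words the protocol already uses. It makes patients with untried standard therapy ineligible for expansion, but Section 1.1 as it stands already places them outside the study population. The alternative costs a short rationale and a few additional tables or listings, using prior-therapy data that the study already collects.
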